4.2.3 Rationale for Endpoints

4.2.3.1 Efficacy Endpoints

Part A LS-SCLC: The primary endpoint is safety in order to establish the MTD of MK-3475 with concurrent chemo and radiation. The primary acute toxicity for chemo and radiation is esophagitis with a rate of $\geq 32\%$ ⁸. While the long term toxicity rate of grade 3 pneumonitis is around 13%⁹.

Part B ES-SCLC: The primary endpoint is safety in order to establish the MTD of MK-3475 with concurrent radiation. The primary acute toxicity for chemo and radiation is esophagitis with a rate of $\geq 32\%$ ⁸. While the long term toxicity rate of grade 3 pneumonitis is around 13%⁹.

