5.6.1.1 Supportive Care Guidelines for Events of Clinical Interest and Immune-related Adverse Events (irAEs) (Appendix 13.4)

Events of clinical interest of a potential immunologic etiology (irECIs) may be defined as an adverse event of unknown etiology, associated with drug exposure and is consistent with an immune phenomenon. irAEs may be predicted based on the nature of the MK-3475 compound, its mechanism of action, and reported experience with immunotherapies that have a similar mechanism of action. Special attention should be paid to AEs that may be suggestive of potential irAEs. An irAE can occur shortly after the first dose or several months after the last dose of treatment.

If an irAE is suspected, efforts should be made to rule out neoplastic, infectious, metabolic, toxin or other etiologic causes prior to labeling an adverse event as an irAE. Information on how to identify and evaluate irAEs has been developed and is included in the Event of Clinical Interest and Immune-Related Adverse Event Guidance Document located in the Administrative Binder. Subjects who develop a Grade 2 or higher irAE should be discussed immediately with the Sponsor.

Recommendations to managing irAEs not detailed elsewhere in the protocol are detailed in Table 6.

Table 6 General Approach to Handling irAEs

irAE	Withhold/Discontinue MK-3475?	Supportive Care
Grade 1	No action	Provide symptomatic treatment
Grade 2	May withhold MK-3475	Consider systemic corticosteroids in addition to appropriate symptomatic treatment
Grade 3 and Grade 4	Withhold MK-3475 Discontinue if unable to reduce corticosteroid dose to < 10 mg	Systemic corticosteroids are indicated in addition to appropriate symptomatic treatment. May utilize 1 to 2 mg/kg prednisone or equivalent per day.

	per day prednisone equivalent within 12 weeks of toxicity	Steroid taper should be considered once symptoms improve to Grade 1 or less and tapered over at least 4 weeks.
--	---	--

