6.0 TRIAL FLOW CHART

6.1 Study Flow Chart (All scheduled tests will be given a window of +/- 3 days)

Treatment Cycle/Title:	Main Study Screening	1	2	3	4	5	6-16 (additional 16 cycles, for eligible patients)	Post MK-3475 Follow up	Survival Follow-Up (>2yrs) ^a
Scheduling Window (Days):	-28 to -1		± 3	± 3	± 3	± 3	± 3	Every 12 weeks post discon	Every 12 weeks
Administrative Procedures									
Informed Consent	X								
Medical History	X								
Concomitant Medication Review	X	X	X	X	X	X	X	X ^a	
Trial Treatment Administration		X	X	X	X	X	X		
Survival Status								X ^{a, f}	X ^{a, f}
Clinical Procedures/Assessments									
Review Adverse Events		X	X	X	X	X	X		
Directed Physical Examination	X	X	X	X	X	X	X		
Vital Signs and Weight	X	X	X	X	X	X	X		
ECOG Performance Status	X								
Laboratory Procedures/Assessments: Analysis Performed by LOCAL Laboratory									
Pregnancy Test – Urine or Serum β-HCG	X ^d								
PT/INR and aPTT	X								
CBC with Differential	X	X ^f							
Comprehensive Serum Chemistry Panel (BMP)	X	X	X	X	X	X	X		
T3, FT4 and TSH ^b	X ^b		X ^b		X ^b		X ^b		
PFT's	X							X ^{c, f}	
Biopsy ^e		X ^g							

Treatment Cycle/Title:	Main Study Screening	1	2	3	4	5	6-16 (additional 16 cycles, for eligible patients)	Post MK-3475 Follow up	Survival Follow-Up (>2yrs) ^a
Scheduling Window (Days):	-28 to -1		± 3	± 3	± 3	± 3	± 3	Every 12 weeks post discon	Every 12 weeks
Blood Biomarker Testing ^e	X	X	X	X	X	X	X	X	
Efficacy Measurements									
Tumor Imaging (CT or PET scan) ^e	X				X		X ^f	X ^{e, f}	X ^{e, f}

- a. Can be done over the phone.
- b. Thyroid functions will be performed with every other MK-3475 cycle, if the first three test are WNL then it can be stopped.
- c. Optional biopsy after radiation treatment
- d. Within 2 weeks of study entry for women with child bearing potential.
- e. Imaging should be performed approximately every 12 weeks (± 4 weeks).
- f. standard of care
- g. Within 3 months of study entry

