7.1.4.3 Post-Treatment Visits

Following the completion of this study, patients will follow up one month later with new imaging studies to assess response to treatment. At this time we will also perform a physical exam, vitals, medication review, and assess for any prior and or new toxicities and or side effects. Following this the same assessment will be performed every three months for the next 2 years and then every 6 months after that.

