7.2 Assessing and Recording Adverse Events

An adverse event is defined as any untoward medical occurrence in a patient or clinical investigation subject administered a pharmaceutical product and which does not necessarily have to have a causal relationship with this treatment. An adverse event can therefore be any unfavorable and unintended sign (including an abnormal laboratory finding, for example), symptom, or disease temporally associated with the use of a medicinal product or protocol-specified procedure, whether or not considered related to the medicinal product or protocol-specified procedure. Any worsening (i.e., any clinically significant adverse change in frequency and/or intensity) of a preexisting condition that is temporally associated with the use of the Merck's product, is also an adverse event.

Changes resulting from normal growth and development that do not vary significantly in frequency or severity from expected levels are not to be considered adverse events. Examples of this may include, but are not limited to, teething, typical crying in infants and children and onset of menses or menopause occurring at a physiologically appropriate time.

Merck product includes any pharmaceutical product, biological product, device, diagnostic agent or protocol-specified procedure, whether investigational (including placebo or active comparator medication) or marketed, manufactured by, licensed by, provided by or distributed by Merck for human use.

Adverse events may occur during the course of the use of Merck product in clinical trials or within the follow-up period specified by the protocol, or prescribed in clinical practice, from overdose (whether accidental or intentional), from abuse and from withdrawal.

Adverse events may also occur in screened subjects during any pre-allocation baseline period as a result of a protocol-specified intervention, including washout or discontinuation of usual therapy, diet, placebo treatment or a procedure.

All adverse events will be recorded from the time the consent form is signed through 30 days following cessation of treatment and at each examination on the Adverse Event case report forms/worksheets. The reporting timeframe for adverse events meeting any serious criteria is described in section 7.2.3.1.

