7.2.3 Immediate Reporting of Adverse Events to the Sponsor and to Merck

7.2.3.1 Serious Adverse Events

A serious adverse event is any adverse event occurring at any dose or during any use of Merck's product that:

- Results in death;
- Is life threatening;
- Results in persistent or significant disability/incapacity;
- Results in or prolongs an existing inpatient hospitalization;
- Is a congenital anomaly/birth defect;
- Is a new cancer (that is not a condition of the study);
- Is associated with an overdose;
- Is another important medical event

Refer to Table 10 for additional details regarding each of the above criteria.

Progression of the cancer under study is not considered an adverse event unless it results in hospitalization or death.

Any serious adverse event, or follow up to a serious adverse event, including death due to any cause other than progression of the cancer under study that occurs to any subject from the time the consent is signed through 90 days following cessation of treatment, or the initiation of new anti-cancer therapy, whichever is earlier, whether or not related to Merck product, must be reported within 24 hours to the Sponsor and within 2 working days to Merck Global Safety.

Non-serious Events of Clinical Interest will be forwarded to Merck Global Safety and will be handled in the same manner as SAEs.

Additionally, any serious adverse event, considered by an investigator who is a qualified physician to be related to Merck product that is brought to the attention of the investigator at any time outside of the time period specified in the previous paragraph also must be reported immediately to the Sponsor and to Merck.

SAE reports and any other relevant safety information are to be forwarded to the Merck Global Safety [contact]

A copy of all 15 Day Reports and Annual Progress Reports is submitted as required by FDA, European Union (EU), Pharmaceutical and Medical Devices agency (PMDA) or other local regulators. Investigators will cross reference this submission according to local regulations to the Merck Investigational Compound Number (IND, CSA, etc.) at the time of submission. Additionally investigators will submit a copy of these reports to Merck & Co., Inc. (Attn: Worldwide Product Safety; [contact]) at the time of submission to FDA.

All subjects with serious adverse events must be followed up for outcome.

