Subjects should be assessed for possible ECIs prior to each dose. Lab results should be evaluated and subjects should be asked for signs and symptoms suggestive of an immune-related event. Subjects who develop an ECI thought to be immune-related should have additional testing to rule out other etiologic causes. If lab results or symptoms indicate a possible immune-related ECI, then additional testing should be performed to rule out other etiologic causes. If no other cause is found, then it is assumed to be immune-related.

ECIs that occur in any subject from the date of first dose through 90 days following cessation of treatment, or the initiation of a new anticancer therapy, whichever is earlier, whether or not related to the Merck’s product, must be reported within 24 hours to the Sponsor and to Merck Global Safety within 2 working days.

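### The protocol contradicts itself on recording late adverse events; if the 30/90-day rules govern, late toxicity is tabulated over windows that depend on when and why MK-3475 stopped

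*Combined protocol and SAP*

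**What the plan says.** Safety is the primary objective (Section 3.1). Section 4.2.3.1 gives the reference toxicity for both parts: "While the long term toxicity rate of grade 3 pneumonitis is around 13" percent. Section 5.6.1.1 adds: "An irAE can occur shortly after the first dose or several months after the last dose of treatment".

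Several sections close or omit late recording:

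- Section 7.2: "All adverse events will be recorded from the time the consent form is signed through 30 days following cessation of treatment". Sections 5.8 and 7.1.5.3.1 also set a 30-day limit for AEs and a 90-day limit for SAEs.
- Section 7.2.3.1, for SAEs: "from the time the consent is signed through 90 days following cessation of treatment, or the initiation of new anti-cancer therapy, whichever is earlier".
- Section 7.2.3.2, for ECIs, from first dose: "through 90 days following cessation of treatment, or the initiation of a new anticancer therapy, whichever is earlier". Pneumonitis of Grade 2 or higher is an ECI.
- Section 6.1: the row "Review Adverse Events" is marked for the treatment cycles and left blank in both follow-up columns.
- Section 7.1.4.4 describes follow-up by imaging and disease status. Section 7.1.4.4.1 moves patients who progress or start new therapy to 12-weekly telephone calls about survival.

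Other provisions point the other way:

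- The 7.2 sentence goes on "and at each examination on the Adverse Event case report forms/worksheets".
- Section 7.1.2.1 has adverse events graded and recorded in the follow-up period as well as during the study.
- Section 7.1.4.3 assesses existing and new toxicity at one month. It then says "Following this the same assessment will be performed every three months for the next 2 years", with six-monthly visits after that.
- Section 7.1.5.3.1 follows events above Grade 1 to resolution or new therapy.
- Section 7.2.3.1 keeps SAEs judged related to the Merck product reportable at any time.

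**The concern.** The protocol names a late radiation toxicity under its safety endpoint and accepts that immune toxicity can appear months after the last dose. It does not say consistently whether such events are recorded. One site or data manager could follow the flow chart and the 30/90-day limits; another could follow 7.1.2.1 and 7.1.4.3. Both would be within the protocol, and their safety data would differ.

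Under the narrow reading, the recording window is anchored to the end of treatment, so its length depends on when and why the patient stopped. That is informative: Table 7 ends MK-3475 for Grade 3-4 drug-associated pneumonitis, confirmed progression generally ends treatment (Section 5.8), and new therapy cuts the SAE/ECI window further. Section 9.2.3 tabulates frequencies of recorded events and makes no allowance for time observed, so a late event that was never recorded counts as no event.

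**Working it through.** The plan gives no figure that depends on these windows, so there is nothing to reproduce. The check is a calendar calculation followed by a comparison of the provisions.

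**Window length under the 30/90-day rules**

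Inputs: dosing every 3 weeks for 16 cycles (Table 2); 30 days for AEs (7.2); 90 days for SAEs and ECIs (7.2.3.1, 7.2.3.2). Assumptions: cessation of treatment means the last MK-3475 dose (7.2 does not define it), there are no dose delays, and no new therapy starts within the window.

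Last-dose day = 1 + 21 × (doses − 1). AE window end = last-dose day + 30. SAE/ECI window end = last-dose day + 90.

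| Doses | Last dose | AE window ends | SAE/ECI window ends |
|---|---|---|---|
| 1 | day 1 | day 31 | day 91 |
| 2 | 1 + 21 = day 22 | 22 + 30 = day 52 | 22 + 90 = day 112 |
| 4 | 1 + 63 = day 64 | day 94 | day 154 |
| 8 | 1 + 147 = day 148 | day 178 | day 238 |
| 16 | 1 + 315 = day 316 | 316 + 30 = day 346 | 316 + 90 = day 406 |

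A patient who stops after two doses therefore has a window 346 − 52 = 294 days shorter than one who completes 16. For Grade 2 or higher pneumonitis the last column applies, because it is an ECI.

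**Scale**

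At the 13% in Section 4.2.3.1, 0.13 × 40 = 5.2 grade 3 pneumonitis cases would be expected in each part. The documents give neither an early-stopping rate nor an onset-time distribution, so this cannot be turned into a number missed.

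**Do the follow-up provisions settle the matter?**

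- The closing clause of the 7.2 sentence can mean every examination, or only examinations inside the 30-day window. The text does not say which.
- Section 7.1.2.1 ties assessment to the flow chart, or more often if clinically indicated, and refers to 7.2 for recording. The flow chart is blank after treatment and 7.2 gives 30 days.
- Section 7.1.4.3 requires toxicity to be assessed but names no form. It does not say whether it covers patients who have progressed or started new therapy, for whom 7.1.4.4.1 specifies only survival calls.
- Section 7.1.5.3.1 covers events already open and stops at new therapy.
- The any-time rule in 7.2.3.1 is limited to serious events that come to the investigator's attention and are judged related to the Merck product. A late pneumonitis attributed to radiation falls outside it, although the Section 3.1 objective is the safety of MK-3475 given with chemoradiation or radiation.

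**The case against.** The strongest reply is that the protocol does provide for late capture. Read naturally, the end of the 7.2 sentence puts findings at any examination on the AE form. Section 7.1.4.3 schedules such examinations for 2 years and beyond, and 7.1.2.1 says events are recorded in follow-up. Section 7.1 calls the flow chart a summary of procedures that the text describes in detail, so blank cells need not override the text. Patients who stop for toxicity without progressing or starting new therapy stay in scheduled follow-up, and the event that stopped them is already recorded.

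Much of this stands. A reader might infer that recording lasts only 30 days, or that late toxicity is lost. The documents do not support that, given the provisions just listed and the any-time rule for related SAEs. Nor do they support a stated downward bias: 9.2.3 defines no late-toxicity rate, and the direction depends on which provisions sites follow.

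A reader might also try to count missed cases by assuming that 10% to 50% of patients stop early, which places 0.10 × 5.2 = 0.5 to 0.50 × 5.2 = 2.6 pneumonitis cases among them. The stopping rate is invented, the sum assumes stopping is independent of pneumonitis, and the result counts cases exposed to a short window, not cases missed.

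What the reply does not do is remove the conflict. Sections 5.8, 7.1.5.3.1 and 7.2 state the 30-day limit, and 7.1.4.4 describes follow-up without toxicity.

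**Conclusion.** The point holds as an unresolved contradiction in how primary-endpoint data are collected. Sections 5.8, 6.1, 7.1.4.4, 7.1.4.4.1, 7.1.5.3.1, 7.2, 7.2.3.1 and 7.2.3.2 need to be reconciled with 7.1.2.1, 7.1.4.3 and the closing clause of the 7.2 sentence.

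If the narrow reading governs, formal observation differs by 294 days between a two-dose patient and a 16-dose patient, on the no-delay and last-MK-3475-dose assumptions. Late pneumonitis attributed to radiation is the event most at risk of going untabulated. Patients in survival-only follow-up have no scheduled toxicity assessment under any provision, except arguably 7.1.4.3.

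Two limits apply. The number of missed events cannot be estimated from the documents. Dose-escalation decisions are not affected, because DLTs are assessed within 22 days of starting therapy (Section 9.1). What is affected is the later safety profile, which the Section 3.1 hypothesis compares with previous trials. The point should be corrected, but it does not undermine the design.

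**What to change.** - **Flow chart (6.1):** mark adverse-event review in the Post MK-3475 Follow up column.
- **Section 7.2:** state that pneumonitis, esophageal events, and Grade 3 or higher events possibly related to radiation or MK-3475 are entered on the AE case report form at the follow-up visits already scheduled in 7.1.4.3. Define cessation of treatment. Bring 5.8, 7.1.2.1, 7.1.4.4 and 7.1.5.3.1 into line.
- **Section 7.1.4.4.1:** add a toxicity question to the existing 12-weekly calls for patients who have progressed or started new therapy.
- **Section 9.2.3:** report these late events by time from start of radiation, with length of observation shown. Cumulative incidence with death as a competing event is a suitable option; the descriptive plan does not require that particular estimator.

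The cost is some extra form entries, a little call time and one added safety presentation. Attribution will be harder after new therapy starts, so its start date should be shown alongside these events. The change concerns data collection and reporting only.

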7.2.2 Reporting of Pregnancy and Lactation to the Sponsor and to Merck

Although pregnancy and lactation are not considered adverse events, it is the responsibility of investigators or their designees to report any pregnancy or lactation in a subject (spontaneously reported to them), including the pregnancy of a male subject's female partner that occurs during the trial or within 120 days of completing the trial. All subjects and female partners of male subjects who become pregnant must be followed to the completion/termination of the pregnancy. Pregnancy outcomes of spontaneous abortion, missed abortion, benign hydatidiform mole, blighted ovum, fetal death, intrauterine death, miscarriage and stillbirth must be reported as serious events (Important Medical Events). If the pregnancy continues to term, the outcome (health of infant) must also be reported.

Such events must be reported within 24 hours to the Sponsor and within 2 working days to Merck Global Safety. (Attn: Worldwide Product Safety; [contact])

7.2.3 Immediate Reporting of Adverse Events to the Sponsor and to Merck

7.2.3.1 Serious Adverse Events

A serious adverse event is any adverse event occurring at any dose or during any use of Merck's product that:

- Results in death;
- Is life threatening;
- Results in persistent or significant disability/incapacity;
- Results in or prolongs an existing inpatient hospitalization;
- Is a congenital anomaly/birth defect;
- Is a new cancer (that is not a condition of the study);
- Is associated with an overdose;
- Is another important medical event

Refer to Table 10 for additional details regarding each of the above criteria.

Progression of the cancer under study is not considered an adverse event unless it results in hospitalization or death.

Any serious adverse event, or follow up to a serious adverse event, including death due to any cause other than progression of the cancer under study that occurs to any subject from the time the consent is signed through 90 days following cessation of treatment, or the initiation of new anti-cancer therapy, whichever is earlier, whether or not related to Merck product, must be reported within 24 hours to the Sponsor and within 2 working days to Merck Global Safety.

Non-serious Events of Clinical Interest will be forwarded to Merck Global Safety and will be handled in the same manner as SAEs.

Additionally, any serious adverse event, considered by an investigator who is a qualified physician to be related to Merck product that is brought to the attention of the investigator at any time outside of the time period specified in the previous paragraph also must be reported immediately to the Sponsor and to Merck.

SAE reports and any other relevant safety information are to be forwarded to the Merck Global Safety [contact]

A copy of all 15 Day Reports and Annual Progress Reports is submitted as required by FDA, European Union (EU), Pharmaceutical and Medical Devices agency (PMDA) or other local regulators. Investigators will cross reference this submission according to local regulations to the Merck Investigational Compound Number (IND, CSA, etc.) at the time of submission. Additionally investigators will submit a copy of these reports to Merck & Co., Inc. (Attn: Worldwide Product Safety; [contact]) at the time of submission to FDA.

All subjects with serious adverse events must be followed up for outcome.

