3.0 OBJECTIVE(S) & HYPOTHESIS(ES)

3.1 Primary Objective(s) & Hypothesis(es)

- (1) **Objective:** Safety of MK 3475 plus chemo/radiation for LS-SCLC and safety of MK 3475 plus radiation for ES-SCLC

Hypothesis: MK-3475 with chemoradiation for LS-SCLC and with radiation for ES-SCLC will demonstrate an acceptable toxicity profile comparable to previous trials

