7.1.5.3.1 Safety Follow-Up Visit

The mandatory Safety Follow-Up Visit should be conducted approximately 30 days after the last dose of trial treatment or before the initiation of a new anti-cancer treatment, whichever comes first. All AEs that occur prior to the Safety Follow-Up Visit should be recorded. Subjects with an AE of Grade > 1 will be followed until the resolution of the AE to Grade 0-1 or until the beginning of a new anti-neoplastic therapy, whichever occurs first. SAEs that occur within 90 days of the end of treatment or before initiation of a new anti-cancer treatment should also be followed and recorded.

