All patients who receive any MK-3475 will be considered evaluable for response and will be included in the efficacy data set.

DLT is defined as any:

- DLTs are defined as any adverse event(s) considered related to the combination of MK-3475 plus radiation as described below:
 - Any \geq Grade 3 bronchospasm or other hypersensitivity reaction;
 - Any other \geq Grade 3 non-skin related adverse event with the exception of laboratory abnormalities;
 - Any Grade 4 laboratory abnormalities, except AST, ALT, or total bilirubin;
 - AST or ALT $> 8 \times$ ULN,
 - Total bilirubin $> 5 \times$ ULN;
 - Any other Grade 4 adverse event;
- 1. Any adverse event, laboratory abnormality or intercurrent illness which, in the judgment of the investigator, presents a substantial clinical risk to the subject with continued study drug dosing;
- 2. Subject experiences an allergic/infusion reaction while receiving study drug at a slower infusion rate due to a prior allergic/infusion reaction;
- 3. Any motor neurologic toxicity \geq Grade 3 regardless of causality;
- 4. Any \geq Grade 3 treatment-related sensory neurologic toxicity.
- 5. Drug related toxicity that prevents administration of MK-3475 for > 21 days from the scheduled dose
 - The time frame for DLT assessment will be within 22 days of therapy initiation.
 - Any grade 4 neutropenia (with or without fever and/or sepsis) or thrombocytopenia (with or without bleeding) lasting at least 1 week or longer (as defined by the NCI-CTC v4.0).
 - Any other grade 3 non-hematologic toxicity including symptoms/signs of vascular leak or cytokine release syndrome; or any severe or life-threatening complication or abnormality not defined in the NCI-CTCAE v4.0 that is attributable to the therapy.

9.2.1. *Statistical Analysis*

Descriptive statistics will be computed for all relevant outcomes, including toxicity, tumor response, PFS, OS, and biomarker response. Descriptive analysis will include a global assessment of patient outcomes for parts A and B separately. All patients receiving at least 1 treatment with MK-3475 will be included in the analysis.

9.2.2. *Demographics and Baseline Characteristics*

Frequency distributions of gender and race will be tabulated by dose/cohort. Summary statistics for age, body weight, height, and Body Mass Index (BMI) will be tabulated by dose/cohort.

9.2.3. *Safety Analyses*

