All recorded adverse events will be recorded per MDACC guidelines using CTCAE Version 4.0. Frequency of adverse events will be tabulated by grade, type, and dose/cohort. Relative frequencies and confidence intervals will also be constructed.

9.2.4. *Efficacy Analyses*

Efficacy data from part A and part B will be performed using the criteria below.

1. **Global irRC:** irRC that factors all lesions both index and non-index.
2. **In-Field irRC:** irRC in which only XRT-treated lesions will be considered and non-index lesions arising inside the XRT PTV
3. **Out-Field irRC:** irRC in which only non XRT-treated lesions will be considered and non-index lesions arising outside the XRT PTV

Time-to-event distributions for PFS and OS will be estimated via Kaplan-Meier analysis. Summary statistics will be computed along with confidence intervals. The limited sample size precludes formal statistical comparison with historical controls.

9.2.5. *Sample Size/Accrual Rate*

The maximum planned number of patients will be 80, with 40 patients being treated with LS-SCLC and 40 patients with ES-SCLC. It is estimated that approximately 1.5 patients per month (for both LS-SCLC and ES-SCLC) will be accrued over 26 months. With 40 patients, the probability of seeing at least one patient with toxicity if the true toxicity rate is 0.1 is 88%. The 95% binomial confidence interval for 6/20 (30%) extends from 15% to 52%.

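### Fatal progression has two statuses in Section 7.2.3.1, and the Section 9.2.3 safety table has no split to keep progression deaths and admissions out of its grade counts

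*Combined protocol and SAP*

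**What the plan says.** The primary objective (Section 3.1) is "Safety of MK 3475 plus chemo/radiation for LS-SCLC and safety of MK 3475 plus radiation for ES-SCLC". Its hypothesis is an acceptable toxicity profile, comparable with that of earlier trials.

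Section 7.2.3.1 contains two statements on progression. The definition is: "Progression of the cancer under study is not considered an adverse event unless it results in hospitalization or death". The paragraph after it covers any serious adverse event from consent to 90 days after treatment or the start of new anti-cancer therapy, "including death due to any cause other than progression of the cancer under study". Such events "must be reported within 24 hours to the Sponsor and within 2 working days to Merck Global Safety".

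Recording is governed elsewhere. Section 7.2 says: "All adverse events will be recorded from the time the consent form is signed through 30 days following cessation of treatment". Section 7.1.5.3.1 extends recording to "SAEs that occur within 90 days of the end of treatment" or until new anti-cancer treatment. Neither section makes an exception for progression.

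The planned analysis in Section 9.2.3 is: "Frequency of adverse events will be tabulated by grade, type, and dose/cohort". Relative frequencies and confidence intervals are to be added. The section does not separate related from unrelated events and gives no rule for progression events. Table 10 (Section 7.2.4) does require a judgment, for each event, of whether the Merck product caused it.

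**The concern.** There are two linked problems. First, the definition and the reporting paragraph disagree about a patient who dies of small cell lung cancer within the reporting period. The definition makes the death a serious adverse event, while the next paragraph takes it out of the deaths needing expedited notice. A site cannot tell from the text whether the notice is due.

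Second, and more important for the analysis, the definition brings progression events into the safety data and Section 9.2.3 has no step that takes them out again or shows them apart. Table 10 makes a fatal event grade 5 and puts an indication for hospitalization in the description of grade 3. Deaths and admissions caused by the cancer would thus be counted in the same grade 3 to 5 frequencies as esophagitis or pneumonitis. With safety as the primary endpoint and no control group, a reader of those frequencies could not tell how much is toxicity and how much is disease.

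**Working it through.** The plan gives no figure on this point, so there is none to reproduce. The check is first a comparison of the text.

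| Source | What it governs | Fatal progression | Progression with admission |
|---|---|---|---|
| 7.2.3.1, definition | Whether progression is an adverse event | Yes, and serious | Yes, and serious |
| 7.2.3.1, next paragraph | Notice within 24 hours (Sponsor) and 2 working days (Merck) | Excepted | Required |
| 7.2 | Recording of adverse events to 30 days | Recorded | Recorded |
| 7.1.5.3.1 | Recording of serious events to 90 days or new treatment | Recorded | Recorded |
| 9.2.3 | Frequencies by grade, type and dose/cohort | Counted | Counted |

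The only disagreement is in the fatal column, between the first two rows. The admission column is consistent throughout. The last three rows show that the mixing comes from the definition combined with a table that has no split. It does not come from the exception on expedited notice.

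The windows matter. Under Section 5.8, confirmed progression normally ends trial treatment, with an exception for some clinically stable or improved patients. The 30-day and 90-day periods are therefore often running just after progression. Events later than that, or after new anti-cancer therapy has begun, fall outside.

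**Illustration of size.** The counts of progression events below are assumptions; the 40 patients per part come from Section 9.2.5. Exact (Clopper-Pearson) 95% limits for x events in n patients are:

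- lower limit: the 0.025 quantile of Beta(x, n − x + 1), or 0 if x = 0
- upper limit: the 0.975 quantile of Beta(x + 1, n − x)

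Grade 5 events in one part, n = 40:

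- x = 0: 0%, upper limit 1 − 0.025^(1/40) = 8.8%
- x = 1: 1/40 = 2.5% (0.1% to 13.2%)
- x = 2: 2/40 = 5% (0.6% to 16.9%)

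Grade 3 or higher, supposing 12 of 40 patients have true toxicity:

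- 12/40 = 30% (16.6% to 46.5%)
- with 2 further patients who have only a progression event: 14/40 = 35% (20.6% to 51.7%)

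The table is also broken down by dose, and Section 9.1 treats 3 or 6 patients at a dose level during escalation. One progression death recorded as grade 5 would show there as 1/3 = 33% or 1/6 = 17%.

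**The case against.** The strongest reply is that this is mostly editorial. The exception concerns expedited notice only, so a reader who infers that progression deaths drop out of the safety table, or enter it depending on which sentence a site follows, goes further than the text. Sections 7.2 and 7.1.5.3.1 still require them to be recorded. That stands. One could also say that a phrase introduced by *including* excludes nothing, so that the general words still catch a progression death. But then the qualifier about progression has no function, and two available readings are themselves a reason to reconcile.

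A reader might also infer that progression admissions are in conflict. They are not: both statements treat them as reportable.

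A further tempting inference is that progression could be scored as dose-limiting through the motor neurologic item, which applies at "Grade 3 regardless of causality". The documents give this little support. The main definition of dose-limiting toxicity requires relatedness to the combination, assessment is limited to 22 days, and active CNS metastases are excluded at entry. That item would also read the same whatever Section 7.2.3.1 said.

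On the table, it is fair that an all-cause table is a legitimate choice, that tabulation by type would show progression on its own line if it is coded as such, and that the causality data allow a related-only table. The named benchmarks in Section 4.2.3.1, esophagitis and grade 3 pneumonitis, are unaffected. However, the plan has no coding rule for progression events and no related-only table. An event coded by its symptom would not be visible as progression, and the overall grade frequencies would still contain it.

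Finally, taking progression events out of adverse event capture altogether would rest on investigator attribution in an open-label, uncontrolled trial. That objection is sound, and the fix below does not do it.

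**Conclusion.** The point holds in a limited form. The two statements in Section 7.2.3.1 conflict for fatal progression only, and only over expedited notice. Separately, the plan as written counts progression deaths and admissions within the recording windows in the grade 3 to 5 frequencies and intervals of the primary safety analysis, with nothing to distinguish them from toxicity.

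The size cannot be derived from the documents, which give no rate of progression death or admission within the windows. The illustration of 5% against 0% grade 5 rests on an assumed 2 deaths among 40 patients and on sites recording as Sections 7.2 and 7.1.5.3.1 require. Any wide range for the effect would be guesswork. The documents do not support the inference that dose decisions are materially exposed.

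**What to change.** 1. In Section 7.2.3.1, reconcile the two statements so that fatal progression has one status for both the adverse event definition and expedited reporting. Either status would remove the conflict, provided that both statements agree.
2. In Section 9.2.3, tabulate treatment-related adverse events beside all adverse events, using the causality judgment already collected under Table 10. List hospitalizations and deaths due to SCLC progression separately, by cause, and do not count them in the toxicity grade frequencies.
3. State that any event to which study treatment may have contributed is still recorded and counted as an adverse event.

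The cost is a short text change, one extra table with its listing, a cause-of-death entry if the forms do not already have one, and a few borderline attribution judgments. Because the progression events stay recorded and listed, a reader who disagrees with an attribution can add the event back.
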